9.4 Study Drug Dosage/Dosage Regimen

Patients will be randomly assigned through the IRT system to an active dose group of 1 mg/kg AK002 followed by 5 doses of 3 mg/kg or placebo. The exact dose will be calculated prior to each infusion and based on current patient weight. Study drug will be administered as a single peripheral IV infusion using an infusion pump as indicated in the study Pharmacy Manual on Days 1, 29 (±3), 57 (±3), 85 (±3), 113 (±3), and 141 (±3).

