11.2.4 Esophago-Gastro-Duodenoscopy with Biopsy

An EGD with biopsy will be performed during the screening period and on Day 169 (± 3 days) or 28 (± 3) days after the last dose of study drug if ET. If the last infusion on Day 141 occurs outside the protocol-specified window, the EGD date should be moved so that it occurs 28 (± 3) days from the date of the last dose, even if this does not fall on Day 169 (± 3 days). Biopsy samples will be collected according to standardized instructions and will be sent to the central laboratory (or designee) for fixing and staining. A blinded central reader will report, among other things, maximum number of eosinophils per hpf and maximum number of tryptase-positive mast cells per hpf, and gastric biopsies will be graded using the Sydney System on inflammation, metaplasia, atrophy, and reactive gastropathy. The Marsh Scale Classification will be used to grade duodenal samples.

Post-treatment EGD results will not be provided to the Investigator and Sponsor until after database lock. The Safety Monitor will review the EGD results and report any issues for escalation to the Medical Monitor and the clinical site, as appropriate, while maintaining the blind.

The screening EGD will be used to determine the following inclusion/exclusion criteria, and the results must be available from the central reader before the patient's eligibility can be verified.

- Inclusion Criterion #3: Baseline endoscopic biopsy with ≥ 30 eosinophils/hpf in 5 hpf in the stomach and/or ≥ 30 eosinophils/hpf in 3 hpf in the duodenum.
- Exclusion Criterion #5: Active *Helicobacter pylori* infection, unless treated and confirmed to be negative prior to randomization and histology per repeat EGD and symptoms still qualify for enrollment after treatment.

Note: A diagnosis of active *H. pylori* at screening may be treated with standard therapies and a repeat EGD completed prior to enrollment to verify that histology criteria are still met and symptoms remain consistent. If *H. pylori* is still present on repeat EGD but UBT and other clinical assessments of active infection are negative, the patient may be randomized into the study.

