15.6 Efficacy Analysis

15.6.1 Primary Efficacy Endpoint Analysis

The first co-primary endpoint will be analyzed using Fisher's exact test. Patients who experience an ICE (i.e., exit the study prematurely or initiate prohibited or restricted medication) prior to the end of Week 24 will be treated as non-responders. Proportion of responders and the associated 95% CI will be presented for each treatment group. The between group difference and the associated 95% CI will also be computed and presented. Sensitivity analysis may be carried out using the Cochran-Mantel-Haenszel (CMH) test stratified by the randomization stratification

factors (Baseline TSS [<28 vs ≥ 28] and disease strata [EG \pm EoD vs EoD]) to assess robustness of Fisher's exact test results.

The rationale for specifying Fisher's exact test as the primary analysis as opposed to specifying CMH is because when a stratum has 100% response for 1 treatment group and 0% response for another treatment group, the CMH test may lose efficiency or not be computable. This is evident from the Phase 2 study outcome.

The second co-primary endpoint will be analyzed by ANCOVA using the imputed data set outlined in the SAP. The LSM, SE, and 95% CI for each treatment group and for the between group difference will be derived from ANCOVA with treatment as a factor, and Baseline PRO TSS (continuous) and EoD without EG (categorical) as covariates. The hypothesis test for the treatment effect will be carried out by the F-test. The synthesizing method will be used to combine the results from multiple imputations.

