- During the Treatment period, subjects will return to the clinic for study visits as described in the Schedule of Events ([Table 1](#)).
- Subjects will continue to complete daily PRO questionnaires throughout the study and the follow-up period.
- A repeat EGD with biopsy will be performed on Day 169 (± 3) or 28 (± 3) days after last dose of study drug if subject is terminated early.
- Follow-up will occur for 84 (± 3) days after the last dose unless subjects decide to enter a long-term extension study. Follow-up visits for subjects opting not to enter the extension study will occur on Days 176 (± 3), 197 (± 3), and 225 (± 3).
- Subjects who satisfactorily complete through Day 176 of AK002-016 have the option to receive AK002 in a separate open-label extension study if all eligibility criteria for the extension study are satisfied. Subjects who enroll in the AK002-016X extension study prior to Day 197 occurring will not complete the Day 197 or Day 225 procedures under Protocol AK002-016.
- Total study duration is approximately 35–37 weeks. For subjects entering the AK002-016X extension study, the total study duration is approximately 28–37 weeks.

The overall schedule of procedures and assessments are presented in Table 1.

Table 1 Schedule of Assessments

	Screening (18–45 days)		Treatment Period (20 weeks)								Follow-Up Period ³⁰ (12 weeks)			
	Baseline ¹	Prior to Day 1	Dose 1 Day 1	Day 8 (±2 days)	Day 15 (±2 days)	Dose 2 Day 29 (±3 days)	Dose 3 Day 57 (±3 days)	Dose 4 Day 85 (±3 days)	Dose 5 Day 113 (±3 days)	Dose 6 Day 141 (±3 days)	Day 169 (±3 days) or 28 days after last dose if ET	Day 176 (±3 days) or 35 days after last dose if ET ²⁹	Day 197 (±3 days) or 56 days after last dose if ET ²⁹	Day 225 (±3 days) or 84 days after last dose if ET ²⁹
Informed consent	X													
Demographics	X		X											
Medical History	X		X											
Prior/Concomitant Medications	X		X			X	X	X	X	X	X	X	X	X
Body weight and height ²	X		X			X	X	X	X	X		X	X	X
Vital Signs ³	X		X			X	X	X	X	X		X	X	X
10 or 12-lead ECG ⁴	X													
Complete Physical Exam ⁵	X													
Symptom-Directed Physical Exam ⁶			X			X	X	X	X	X		X	X	X
Baseline Diet Assessment ⁷	X													
Baseline Diet Compliance ⁸			X			X	X	X	X	X		X	X	X
Stool for Ova and Parasite ⁹	X													
ePRO Activation and Training ¹⁰	X													
ePRO Questionnaire (may include Additional Questions) ¹¹	<-----Complete electronically one time daily----->													
CCI [REDACTED]	X		X			X	X	X	X	X		X	X	

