Study Day	Study Day 1 is defined as the date on which a subject took the first dose of study drug. Other study days are defined relative to Study Day 1. For visits prior to the first dose of study drug, Study Day is calculated as Visit Date – Day 1 Date. For visits after the first dose, Study Day is calculated as Visit Date – Day 1 Date +1.
Study Drug	AK002 or placebo administered by IV infusion.
Study Week	Study Week for PRO analysis is defined as 7 days a week starting from the day of first dose (Day 1).
Tissue Eosinophil Responder in Disease Status (2 levels; EG ± EoD, EoD)	For EG with/without EoD subjects: Mean eosinophil count \leq 4 cells/hpf in 5 highest gastric hpf and/or mean eosinophil count \leq 15 cells/hpf in 3 highest duodenal hpf. For EoD subjects: Mean eosinophil count \leq 15 cells/hpf in 3 highest duodenal hpf.
Treatment-emergent	Adverse events reported in the clinical database with a date of onset on or after the start date of the first dose of the study drug.
Treatment Responder	Subject with >30% improvement in TSS from baseline and mean eosinophil count \leq 4 cells/hpf in 5 highest gastric hpf and/or mean eosinophil count \leq 15 cells/hpf in 3 highest duodenal hpf.

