6.12 Analysis of Secondary Efficacy Endpoints

6.12.1 Change in Tissue Eosinophil Count

For subjects who provide gastric or duodenal only biopsy, the calculation will be based on the average count of the highest readings from the respective mucosa at baseline and Day 169 (Week 24). For subjects who provide both gastric and duodenal biopsies, the calculation will be based on the average count of the highest readings from the Day 169 biopsy that corresponds in location (gastric or duodenal) to the location with the highest average count at baseline. The change in tissue eosinophil count from baseline to Day 169 will be analyzed using ANCOVA with treatment as factor, baseline eosinophil counts, baseline PRO TSS, and disease status as covariates. The LSM, SE, and 95% CI for individual treatment groups, and LSM, SE, 95% CI, and p-value for the between treatment difference will be presented.

6.12.2 Proportion of Subjects Achieving Peak Gastric and/or Duodenal Intraepithelial Eosinophil Count of ≤ 1 Cell/hpf

This endpoint will be analyzed using the Fisher's exact test similar to the analysis for the first co-primary endpoint (Section 6.11.1).

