9.2 Appendix 2: Intercurrent Events

A. Use of any of the following prohibited medications during the course of the study as described

- 1) Immunosuppressive or immunomodulatory drugs (e.g., IL-5 modulators, i.e., benralizumab, reslizumab, mepolizumab; IL-4 and IL-13 antagonists, i.e., dupilumab; calcineurin inhibitors, i.e., cyclosporin, tacrolimus; mTOR inhibitors, i.e., sirolimus, everolimus; anti-metabolites, i.e., azathioprine, methotrexate, 6-mercaptopurine, leflunomide, mycophenolate mofetil; alkylating agents, i.e., cyclophosphamide; TNF inhibitors, i.e., infliximab, adalimumab; anti-IgE antibodies, i.e., omalizumab; and eosinophil-depleting drugs, i.e., pramipexole.
 - a) Use at any point during the study.
- 2) Glucocorticoids
 - a) Initiation of any course of treatment or single use of systemic or swallowed corticosteroids at a dose of >10 mg/day prednisone or equivalent starting at Week 21 and through the end of Week 24. This does not include use of corticosteroids given as pre-infusion prophylaxis or treatment of IRR.

B. Use of restricted medications outside the protocol-defined specifications

- 1) Glucocorticoids
 - a) Discontinuation of a previously stable dose of systemic or swallowed corticosteroids (≤ 10 mg/day prednisone or equivalent) after the screening period.
 - b) Initiation of a new course of systemic or swallowed corticosteroids (≤ 10 mg/day prednisone or equivalent) following the screening period and continuing to at least study Week 21 (within 2 weeks of efficacy assessment at Weeks 23 and 24).
- 2) Proton Pump Inhibitors
 - a) Discontinuation of a previously stable dose of an oral PPI after the screening period and before the end of Week 24.
 - b) Initiation or increase in the dose of an oral PPI following the screening period and continuing to at least study Week 21 (within 2 weeks of efficacy assessment at Weeks 23 and 24).
- 3) Sodium cromolyn
 - a) Discontinuation of a previously stable dose of sodium cromolyn after the screening period and before the end of Week 24

- b) Initiation or increase in the dose of sodium cromolyn following the screening period and continuing to at least study Week 22 (within 1 week of efficacy assessment at Weeks 23 and 24).

C. Discontinuation of Investigational Medical Product

- 1) Discontinuation of study agent due to:
 - a) Infusion-related reaction
 - b) Subject withdrawal
 - c) Meeting study withdrawal criteria (Protocol Section 13.10)

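### For biopsies after Day 169, high-dose steroid first used after Week 24 but before the biopsy is not an intercurrent event for the histology co-primary

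*SAP*

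**What the plan says.** - **Steroid rule.** SAP Appendix 2, A.2.a, makes a new course or single use of systemic or swallowed corticosteroid above 10 mg/day an intercurrent event (ICE) when it falls "starting at Week 21 and through the end of Week 24". Infusion prophylaxis and treatment of infusion reactions are exempt. The PPI discontinuation limb (B.2.a) has the same end-point.
- **Study week.** SAP 4.1: "Study Week for PRO analysis is defined as 7 days a week starting from the day of first dose (Day 1". No other definition of a study week is given.
- **Biopsy date.** SAP 3.1: "A repeat EGD with biopsy will be performed on Day 169", with ±3 days. Protocol 11.2.4 adds: "If the last infusion on Day 141 occurs outside the protocol-specified window, the EGD date should be moved", to 28 ±3 days after that dose. The window for infusion 6 is in Protocol 9.4: "85 (±3), 113 (±3), and 141 (±3").
- **Consequence of an ICE.** Under SAP 5.4.1, a tissue count taken after an ICE is set to missing; without an earlier postbaseline count the patient is a treatment failure. Under Protocol 15.6.1, patients with an ICE "prior to the end of Week 24 will be treated as non-responders".
- **A competing label.** SAP 6.12.1 refers to counts "from the respective mucosa at baseline and Day 169 (Week 24"), and Protocol 15.6.2 uses the same label.
- **Rationale.** The text closing SAP Appendix 2 says that corticosteroids and PPIs may affect tissue eosinophil counts as well as symptoms, and that new use running close to the evaluation period should be treated as intercurrent.

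**The concern.** One calendar window serves two co-primary endpoints measured at different times. It closes when the symptom diary period closes. The biopsy can come later, and the Protocol moves it further when infusion 6 is late, but no passage moves the ICE window with it.

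The first co-primary endpoint is a threshold on tissue eosinophils, which the SAP itself says steroids may change. Protocol 8.1 and 8.2 permit use above 10 mg/day for an unrelated medical condition, so such use can occur without a protocol violation. A count taken on newly started high-dose steroid could then stand as a valid Week 24 result in either arm. What is at stake is the correct classification of individual responders.

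**Working it through.** **The plan's own figure, for context.** SAP 3.5 states more than 99% power for 0.6 versus 0.1 with 80 per arm, two-sided 0.05. The normal approximation gives 0.99999998 and exact enumeration of Fisher's test gives 0.9999999, so the figure is reproduced.

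**Study weeks.** Week w runs from Day 7(w−1)+1 to Day 7w.
- Week 21: Days 141–147
- Weeks 23–24: Days 155–168
- Week 24: Days 162–168, so the steroid window is Days 141–168
- Day 169 is the first day of Week 25

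**Uncovered full days.** For a biopsy on Day b, the full days after the window and before the biopsy day number max(0, b − 1 − 168). When infusion 6 is late, on Day d ≥ 145, the EGD falls on Days d+25 to d+31, so the range is d − 144 to d − 138.

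| Infusion 6 | Permitted EGD days | Uncovered full days |
|---|---|---|
| In window (Days 138–144) | 166–172 | 0 for Days 166–169; 1, 2, 3 for Days 170, 171, 172 |
| Day 145 | 170–176 | 1–7 |
| Day 148 | 173–179 | 4–10 |
| Day 151 | 176–182 | 7–13 |
| Day 155 | 180–186 | 11–17 |

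Subtracting 168 from the biopsy day gives one more in each case, because it counts the biopsy day itself.

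**If Day 169 is counted as Week 24.** Each non-zero figure falls by one: 0, 1 and 2 for Days 170–172, and 3–9 for infusion 6 on Day 148. Same-day use on Day 169 is then covered.

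**Example.** Infusion 6 is on Day 148 and the EGD is on Days 173–179. A single non-exempt high-dose use on Day 141, 32–38 days before the biopsy, voids the count. A high-dose course started on Day 170, 3–9 days before it, does not.

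**Contrast with the low-dose limb.** B.1.b covers a new course at or below 10 mg/day that continues to at least Week 21, and gives no end date. Read literally, a low-dose course started on Day 170 before a Day 172 biopsy is an ICE under the SAP, while a high-dose course is not.

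**Size per patient.** One reclassified patient moves an arm by 1/80 = 1.25 percentage points, against an assumed placebo rate of 10% (8 of 80).

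**Effect on power.** Under assumed shifts, exact Fisher power is 0.9994 with the placebo rate raised from 0.10 to 0.20, and 0.99993 with the AK002 rate cut from 0.60 to 0.50.

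**A related mismatch.** If the biopsy is on Day 166 or 167 and steroid follows it by Day 168, Protocol 15.6.1 gives a non-responder, while SAP 5.4.1 keeps the count because it came before the ICE.

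**The case against.** *For the target visit the rule works.* This stands. For a biopsy on Days 166–169, every preceding day back to Day 141 lies inside the window. Steroid started on Day 168 before a Day 169 biopsy is an ICE. A reader might infer that high-dose steroid just before the biopsy never affects responder status; the documents do not support that.

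*Day 168 is an inference.* The week definition is given for PRO analysis, and both documents label Day 169 as Week 24. This stands in part. It closes Day 169 itself but not later days. One could go further and read Week 24 as the EGD visit whenever it happens, but Appendix 2 does not say so. The ambiguity is a reason to write the window in days.

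*SAP 4.2.4 names prohibited or restricted medication as an ICE with no date limit.* It defers the detail to Appendix 2, so the dated rule governs.

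*Other safeguards exist.* Prohibited use is a protocol deviation (SAP 6.3), is listed separately (SAP 6.10.2), and may lead to per-protocol exclusion on criteria fixed before unblinding (SAP 6.1.4). That helps with use outside the exceptions. It would not reliably catch permitted use for an unrelated condition.

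*The impact is not shown.* This largely stands. A patient must have both a biopsy after Day 169 and new high-dose steroid in the gap. The documents give no frequency for either and no onset time for a steroid effect on tissue counts. Nothing shows that one to three days of steroid would turn a qualifying count into a response.

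**Conclusion.** The concern holds for biopsies after Day 169: Days 170–172 on schedule, or later when the EGD follows an out-of-window infusion 6. For these, systemic or swallowed corticosteroid above 10 mg/day first used after Day 168 and before the biopsy is not an ICE under SAP Appendix 2 A.2.a or Protocol 15.6.1. The count is kept, contrary to the SAP's stated rationale.

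The gap is short for on-time biopsies and grows day for day with a late infusion 6. The longer gaps in the table need a materially late infusion, and their upper ends assume the latest permitted EGD. All counts assume that Week 24 ends on Day 168.

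A reader might also infer that the gap inflates the placebo response or threatens the co-primary result. The documents support neither: either arm may receive steroid, so the direction is unknown, and power stays above 99.9% under the shifts examined. This is a small but definite error in the classification rule, best settled before unblinding so that no such case has to be decided with treatment known.

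**What to change.** 1. In SAP Appendix 2, A.2.a and B.2.a, split the end of the window by endpoint. For histology endpoints, keep the Week 21 start in A.2.a but end both limbs at the actual date of the Week 24 EGD, counting only use (or, for PPI, discontinuation) before the biopsy. For TSS, leave the end of Week 24 as it is.
2. State Week 24 in study days.
3. Align Protocol 15.6.1 with SAP 5.4.1, so that an ICE after the biopsy is handled the same way in both.
4. State that the composite treatment-responder endpoint (SAP 6.12.3) is a non-response if either component has an ICE.

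Two extensions should be avoided. The cromolyn limb (B.3.a) should not be changed, because the SAP's stated concern there is reported symptoms rather than tissue. A rolling 28-day look-back should not replace the Week 21 start: for a Day 186 biopsy it would begin on Day 158 and drop Days 141–157, which the SAP now covers.

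The cost is a wording change and a derivation from EGD and medication dates that are already collected (Protocol 11.3.1). The downside is that ICE status may differ between the two co-primary endpoints for a few patients.

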8.2 Allowed Medications

Medications, other than those that are prohibited (Section 8.1) such as antihistamines, leukotriene antagonists, and sodium cromolyn, are allowed during the study and, unless required due to unforeseen medical necessity, doses are to remain stable. All medication use during the screening period and throughout the study will be documented in the CRF. Any medications used for the treatment of IRR are not considered deviations from the protocol.

Systemic or swallowed corticosteroids with a dose of ≤ 10 mg/day of prednisone or equivalent are acceptable, as long as the dose remains stable throughout screening and during the study.

The use of systemic or topical corticosteroids with a dose of >10 mg/day of prednisone or equivalent is permitted if it is deemed to be medically necessary to treat an unrelated medical condition or when given as a premedication prior to infusion or to treat an IRR that occurs during infusion.

9. Study Treatment

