Per protocol, subjects are required to remain on stable doses of either PPI or corticosteroids (≤ 10 mg prednisone equivalent per day) throughout the course of the study if they are on a stable dose during the screening period. Because of the potential impact of corticosteroids and PPI on both histologic assessment of tissue eosinophil levels as well as subject reported GI symptoms, subjects must meet the entry requirements for both histology and symptom burden (TSS6) if they are on any of these medications at screening and therefore must remain on a stable dose throughout the study in order to meaningfully interpret any change from baseline during the evaluation phase. Conversely, subjects starting these medications due to unforeseen medical necessity following the screening period and remaining on them through a time point sufficiently close to the evaluation period to potentially impact assessment of symptoms and/or histologic assessments will be considered as intercurrent events. For PPI and corticosteroids (≤ 10 mg/day prednisone or equivalent) a conservative washout period is estimated at 2 weeks, and therefore, continuation of a new course of therapy beyond Week 21 could be considered as a potential ICE.

Sodium cromolyn is a mast cell stabilizer and could potentially impact reported symptoms in a similar way to 1 of the mechanisms of action of AK002. As such, discontinuation of a previously stable dose of sodium cromolyn after the screening period and before the end of Week 24 could be considered as a potential ICE. Likewise, the initiation or increase in the dose of sodium cromolyn following the screening period and continuing to at least study Week 22 (within 1 week of efficacy assessment at Weeks 23 and 24) could be considered as a potential ICE. It is estimated that 1 week would be a sufficient washout period for the effects of sodium cromolyn.

Antihistamines are unlikely to impact histologic assessments in the study but could have slight impact in some symptoms depending on the type, dose, and duration of use. As such, subjects are required to stay on stable doses of antihistamines if they are taking them at the time of screening and to remain on them through completion of the study. Due to unforeseen medical circumstances and acknowledging that some subjects may have concurrent allergic conditions, the use of these medications by some subjects during the study is anticipated.

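### An increase of a stable low-dose corticosteroid that stays at or below 10 mg/day is not a listed intercurrent event, although sustained PPI and cromolyn increases are

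*SAP*

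**What the plan says.** Protocol 4.5.4 leaves the detail of intercurrent events to the SAP, so SAP Appendix 2 is the operative list. Its part B covers restricted medications in three classes.

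- Corticosteroids at or below 10 mg/day: B.1.a is "Discontinuation of a previously stable dose of systemic or swallowed corticosteroids" after screening. B.1.b is "Initiation of a new course of systemic or swallowed corticosteroids (≤ 10 mg/day prednisone or equivalent) following the screening period", provided it continues to at least Week 21.
- PPIs: B.2.b is "Initiation or increase in the dose of an oral PPI following the screening period and continuing to at least study Week 21".
- Sodium cromolyn: B.3.b has the same form as the PPI item, with Week 22 as the cut-off.

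Above the 10 mg/day limit, item A.2.a covers a course or single use "at a dose of >10 mg/day prednisone or equivalent starting at Week 21 and through the end of Week 24", with exceptions for infusion prophylaxis and infusion reactions.

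The rationale that follows the list says that corticosteroids and PPIs may affect both histology and symptoms. Patients on them at screening "therefore must remain on a stable dose throughout the study in order to meaningfully interpret any change from baseline". Protocol 8.2 accepts low-dose corticosteroids only "as long as the dose remains stable throughout screening and during the study".

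**The concern.** The list controls what enters both co-primary analyses. Under SAP 5.4.1 and 5.4.2, eosinophil counts and daily symptom scores are discarded only when collected after an intercurrent event. SAP 4.2.5 applies the same trigger to non-response. A change that is not on the list leaves the data in place.

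The omitted change is a dose increase in a class that the SAP itself names as able to influence both endpoints. The SAP's estimand question is about benefit from study drug when no other medication that could affect the disease is added. Keeping an outcome observed under a raised corticosteroid dose does not answer that question. If such increases were commoner on placebo, the treatment difference would be diluted; if commoner on AK002, it would be inflated.

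The planned sensitivity analyses do not help. The placebo-based and tipping-point analyses in SAP 6.11.5 act on scores collected on or after an intercurrent event, and the listing and table in SAP 6.11 show only recorded events. These patients would appear in neither.

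**Working it through.** **1. The items side by side (SAP Appendix 2)**

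| Class | Stopping a stable dose | Starting | Increasing |
|---|---|---|---|
| Corticosteroid, 10 mg/day or less | Listed (B.1.a) | Listed if continued to at least Week 21 (B.1.b) | Not listed |
| PPI | Listed (B.2.a) | Listed if continued to at least Week 21 (B.2.b) | Listed, same condition |
| Sodium cromolyn | Listed (B.3.a) | Listed if continued to at least Week 22 (B.3.b) | Listed, same condition |

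**2. Tracing a hypothetical patient.** The patient enters on a stable low dose, has it raised in Week 18 without passing 10 mg/day, and stays on the raised dose through Week 24. B.1.a fails because nothing was stopped. B.1.b fails because no new course was started. A.2.a fails because the dose is not above 10 mg/day. No event is recorded, so the Week 24 biopsy and Weeks 23–24 TSS are used as observed.

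**3. What an event would have done.** TSS from that point would be set to missing and multiply imputed (SAP 5.4.2). The Week 24 eosinophil count would be set to missing, then replaced by an earlier unscheduled post-baseline count if one exists. Only without such a count is the patient a treatment failure (SAP 5.4.1).

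**4. A neighbouring gap.** A course above 10 mg/day that begins before Week 21 and is still running in Weeks 23–24 does not match A.2.a, which starts at Week 21. Nor does it match B.1.b, which is limited to 10 mg/day or less.

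**5. The plan's power (SAP 3.5).** Inputs: 80 per arm, difference 7.4, SD 12.5, two-sided alpha 0.05. SE = 12.5 × √(2/80) = 1.976. Power ≈ Φ(7.4/1.976 − 1.96) = Φ(1.784) = 96.3% (96.1% with the noncentral t). The stated 96% reproduces. For 0.6 versus 0.1, Fisher's exact power exceeds 99.99%, consistent with the stated figure of over 99%.

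**6. Size per patient.** A change of responder status moves one arm's rate by 1/80 = 1.25 percentage points. Status changes only if the patient's observed count meets the responder threshold. At the planning rate, 1 − 0.1 = 90% of placebo patients are non-responders either way, before any corticosteroid effect.

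**7. Illustration only.** The documents give no rate of increases and no size of effect. Assume that a share fP of placebo and fA of AK002 patients are raised and that each gains a further g = 3.7 to 7.4 TSS points. The expected difference is D = 7.4 − g × (fP − fA), with power from the formula in step 5.

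| Raised | D | Power |
|---|---|---|
| Placebo 5%, AK002 0% | 7.03–7.22 | 94–95% |
| Placebo 10%, AK002 0% | 6.66–7.03 | 92–94% |
| Placebo 20%, AK002 0% | 5.92–6.66 | 85–92% |
| Placebo 0%, AK002 5% | 7.59–7.77 | 97–98% |
| Placebo 0%, AK002 10% | 7.77–8.14 | 98% |
| Equal shares, equal gain | 7.40 | 96% |

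For the tissue endpoint, suppose raised placebo patients respond at 0.6. The placebo rate taken at face value is (1 − fP) × 0.1 + fP × 0.6, that is 0.125, 0.15 or 0.20 at 5%, 10% or 20%. Counting them as non-responders gives (1 − fP) × 0.1 = 0.095, 0.09 or 0.08. Power stays above 99.9% throughout.

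**The case against.** The best defence is that the appendix should be read as a whole. Part B is headed as use of restricted drugs outside what the protocol specifies, Protocol 8.2 requires a stable dose, and the rationale treats PPIs and corticosteroids together. On that reading an increase is already out of specification and B.1.b merely lacks a few words. This is fair as to intent: a reader might infer that the SAP deliberately accepts corticosteroid-assisted responses, and nothing in the documents supports that. It does not close the gap. The enumerated items are what will be programmed, and the PPI and cromolyn items needed the increase written out under the same heading. The rationale itself speaks only of starting and of new courses, and Protocol 15.6.1 only of initiating.

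The contrast between classes also has limits. A reader might infer that any PPI or cromolyn increase is an event. It is one only if it lasts to Week 21 or Week 22 respectively, and the rationale softens some of these items to possible events.

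There is a partial safeguard. An increase breaches Protocol 8.2 and could lead to exclusion from the per protocol population. That population excludes only major violations, its criteria are still to be set (SAP 6.1.4), and it is used only to check robustness (SAP 6.1.5).

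Finally, increases balanced across arms and similar in effect would cause little or no bias in the difference. That stands.

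**Conclusion.** The gap is real on the current text and should be closed. As listed, a sustained corticosteroid increase within 10 mg/day is not an intercurrent event, so both co-primaries use those outcomes as observed, against the SAP's own reason for requiring a stable dose.

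The size is unknown. A reader might want a count of misclassified patients, but the documents give neither the share entering on low-dose corticosteroid nor the share later raised. Some of those raised would be histology non-responders under either rule. A reader might also infer a bias in favour of AK002; the documents do not fix the direction. What can be said is 1.25 percentage points per patient whose responder status changes, and essentially no effect on tissue-endpoint power. A TSS effect becomes noticeable only under the assumed one-sided imbalances in the illustration. Nothing here shows that either co-primary conclusion would change.

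**What to change.** Before unblinding, reconcile Appendix 2 B.1.b with B.2.b, B.3.b, the appendix rationale and Protocol 8.2. Extend B.1.b so that, besides a new course, a rise above the stable screening dose of a systemic or swallowed corticosteroid counts as an intercurrent event. The conditions stay as they are: a dose at or below 10 mg/day, begun after screening and continuing to at least Week 21.

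In the same edit, state how a course above 10 mg/day that starts before Week 21 and is still running in Weeks 23–24 is classified, since A.2.a and B.1.b as worded both miss it.

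This governs how data are classified and leaves permitted treatment unchanged. The cost is a few words in the SAP; dose and dates of concomitant medication are already collected (Protocol 11.3.1). The small downside is that a few more patients may carry an intercurrent event, with their later TSS imputed and their histology handled under SAP 5.4.1.
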